7.4 Blinding

Not Applicable. It will not be possible to blind the investigator the type of device used

7.5 Emergency unblinding

Not applicable

7.6 Baseline data

Base line data includes gender, age, weight, height, BMI & ASA score

Airway assessment includes Mallampati score, thyromental distance, mouth opening, jaw protrusion and neck movement. This is the routine assessment undertaken by the anaesthetists as a part of standard preoperative airway assessment.

7.7 Trial assessments

- Modified intubation difficulty scale score (Appendix 1)
- Time to successful tracheal intubation: It is time from when the videolaryngoscope is introduced into the oral cavity until the first capnography waveform is obtained.
- Laryngoscopy time: It is time from when the videolaryngoscope is introduced into the oral cavity to best view of the glottis (vocal cords).
- First attempt success rate for tracheal intubation
- Anaesthetist's visual analogue score for ease of use of the bougie

7.8 Long term follow-up assessments

Patients will be reviewed in the first 3 to 24 hours whilst they are in the hospital as apart standard postoperative visit. No further follow up is required for this study.

7.9 Storage and analysis of samples

Not applicable for this study. No biological samples required for this study

7.10 End of study definition

This is defined as the date on which the last patient (patient number 160) will be recruited to the study.

8. STATISTICS AND DATA ANALYSIS

8.1 Sample size calculation

From our previous study using CMAC videolaryngoscope and Frova bougie, mean mIDS was 1.75 and SD was 0.95 [5]. We considered a 30% reduction in mIDS to be clinically relevant. For standardized difference of 0.53, with a power of 0.9 and significance level of 0.05, we need 73 patients in each group. To account for failures and dropouts, we plan to recruit 160 patients in total.

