7.3 Randomisation scheme

Sample size: From our previous study using CMAC VL and Frova bougie, the standard deviation was 0.95 and mean mIDS was 1.75. We considered a 30% reduction in mIDS to be clinically relevant. For standardized difference of 0.53, with a power of 0.9 and significance level of 0.05, we need 73 patients in each group. To account for failures and dropouts, we decided to recruit 160 patients in total.

Randomisation for this study will be completed using sealed opaque envelopes. On arrival to the anaesthetic room, sealed envelope will be opened to reveal the group. Based on the group, following induction of general anaesthesia, the chosen bougie will be selected. It would be ensured that both type of bougies readily available in the airway trolley. Once the bougie is successfully placed in the trachea, tracheal intubation is completed as normal.

On arrival in the anaesthetic room, patients will be monitored using peripheral oxygen saturation, end-tidal CO₂, ECG and blood pressure. Both standard and flexible tip bougies will be kept ready for each study patient. Patient will be randomly allocated to one of two groups.

1. Flexible tip bougie
2. Standard bougie

All patients will be pre-oxygenated in a 15 to 20° head up position, to achieve a fractional ETO₂ of at least 0.8 prior to induction of anaesthesia. General anaesthesia will be induced at the discretion of lead anaesthetist. After the loss of consciousness was achieved, facemask ventilation will be commenced, and anaesthesia will be maintained with a volatile anaesthetic agent (age adjusted minimum alveolar concentration of 1.0) or using total intravenous technique as decided by the lead anaesthetist. Following the confirmation of the onset of neuromuscular blockade

using neuromuscular monitoring, in an optimal head and neck position, laryngoscopy will be performed using the videolaryngoscope as revealed by randomisation.

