8.8 Procedure(s) to account for missing or spurious data

As the study duration is short, we unlikely to miss follow up of patients. All care would be taken to record all necessary data during preoperative visit and during

intubation. Very rarely the surgical plan may change, or surgery may be cancelled after recruiting. In total we need 146 patients to detect a significant difference in the modified intubation difficulty scale score. We have planned to recruit 160 in total to overcome any missing data or loss of follow up.

8.9 Other statistical considerations.

There is no plan to deviate from original statistics

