| Number of alternative intubation techniques, add 1 point for | | | |
| Bougie impingement: N3 =1 | Bougie rotation: N3=2 | | |
| Subglottic tube impingement: N3=3 | Tube rotation: N3=4 | | |
| Other manoeuvre: N3=5 | | | |
| Percentage of Glottis Opening (POGO) | >50%: N4 =0 | <50%: N4=1 | |
| Lifting Force Required | Normal: N5=0 | Increased: N5=1 | |
| External Laryngeal Pressure | Not applied: N6=0 | Applied: N6=1 | |
| Total Score | | | |

Correlation between mIDS and the Degree of Difficulty

[figure not shown]
| mIDS Score | Degree of Difficulty |
|-----------------------|------------------------------|
| mIDS =0 | Easy |
| mIDS =0 < to \leq 5 | Slight difficulty |
| mIDS = >5 | Moderate to Major Difficulty |
| mIDS = ∞ | Impossible intubation |

The percentage of glottic opening (POGO) score

The percentage of glottic opening (POGO) score represents the portion of the glottis visualized. It is defined anteriorly by the anterior commissure and posteriorly by the interarytenoid notch. The score ranges from 0% when none of the glottis is seen to 100% when the entire glottis including the anterior commissure is seen.

APPENDIX 2

Photograph showing flexible tip bougie

[Video](#) demonstrating flexibility of tip of the flexible tip bougie

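### The sample-size reserve counts failures as lost patients and section 2.3 stops data collection at unanticipated difficulty, although Appendix 1 gives impossible intubation the worst, rankable score

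*Protocol*

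**What the plan says.** Section 8.1 states the requirement: "For standardized difference of 0.53, with a power of 0.9 and significance level of 0.05, we need 73 patients in each group". It then adds a reserve: "To account for failures and dropouts, we plan to recruit 160 patients in total". Section 7.3 repeats this almost word for word: "To account for failures and dropouts, we decided to recruit 160 patients in total".

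Section 8.8, on missing or spurious data, gives the same reserve a different purpose: "We have planned to recruit 160 in total to overcome any missing data or loss of follow up". Its examples are a changed surgical plan and a cancelled operation. It does not mention failed intubation.

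Section 2.3 says that at unanticipated difficulty the anaesthetist moves to the Difficult Airway Society guidelines and study data collection ends there. It also leaves the anaesthetist free to choose other airway equipment.

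Appendix 1 grades the primary outcome, and its worst category, mIDS = infinity, is labelled "Impossible intubation". Section 8.3.2 plans a rank test for this outcome (Mann-Whitney, or Kruskal-Wallis).

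**The concern.** An allowance for dropouts covers patients who yield no primary outcome. A cancelled operation is one. A patient who cannot be intubated is different: the outcome has been observed, and on the trial's own scale it is the worst possible. Sections 7.3 and 8.1 put both in the same allowance.

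The distinction matters because failure is not independent of the arm. The Introduction argues that the standard bougie tends to impinge anteriorly and that this raises the chance of failed intubation. Section 2.1 states the hypothesis in terms of intubation success. Leaving failures out would condition the comparison on something the bougie itself influences after randomisation. It could hide a real advantage, or favour a bougie that scores well when it works but fails more often.

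**Working it through.** **1. The plan's own figures.** Section 8.1 gives "mean mIDS was 1.75 and SD was 0.95" and a 30% reduction as the target, that is 0.30 × 1.75 = 0.525 points. At the stated standardised difference of 0.53, with 90% power and two-sided 5% (sidedness is not stated, so two-sided is assumed):

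n per group = 2 × (1.960 + 1.282)² / 0.53² ≈ 74.8, so 75.

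The plan's 73 is reproduced to within 2. The total is 2 × 73 = 146, as in section 8.8. The reserve is 160 − 146 = 14, or 14/160 = 8.75%. It is not split between failures and dropouts.

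**2. The passages side by side.**

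| Place | Status of a failure |
|---|---|
| 7.3 and 8.1 | In the reserve with dropouts, so not among the 146 that count |
| 8.8 | Not named; the same reserve covers missing data and loss to follow-up |
| 2.3 | Data collection stops at unanticipated difficulty |
| Appendix 1 | Impossible intubation has a score, infinity |
| 8.3.2 | A rank test, which can place infinity last |

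The first and third rows lead to the loss of a value that the last two rows can use.

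**3. Size.** Simulated trials had 80 patients per arm. Scores were drawn from a normal distribution with SD 0.9, rounded and floored at 0, and compared by a two-sided Mann-Whitney test at 0.05, with 4000 trials per row. All failure rates are assumptions. A failed case was either ranked worst or dropped.

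| Mean, standard vs flexible | Failures, standard vs flexible | Significant, ranked worst | Significant, dropped |
|---|---|---|---|
| 1.75 vs 1.225 | 2% vs 2% | 90% | 92% |
| 1.75 vs 1.225 | 1% vs 4% | 81% | 92% |
| 1.75 vs 1.225 | 1% vs 8% | 61% | 91% |
| 1.75 vs 1.40 | 8% vs 1% | 82% | 60% |
| 1.75 vs 1.225 | 8.75% vs 8.75% | 79% | 90% |

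The 8% against 1% rows imply 80 × 0.08 + 80 × 0.01 = 7.2 failures, about half the reserve of 14.

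A further set of 3000 trials per scenario used SD 0.95, no shift in scores, and failures of 15% against 2.5% (80 × 0.15 + 80 × 0.025 = 14, the whole reserve). The difference between arms was detected in about 28 to 30% of trials with failures ranked worst. With failures dropped, the rate was 5 to 6.5%, close to the nominal error rate.

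**The case against.** A reader might infer that the trial excludes failed intubations from its primary analysis and replaces them with extra recruits. The text does not support that. The word failures is never defined and could mean a failed intubation, a device fault or a failure to proceed. No passage excludes such patients, no analysis population is stated, and a statistical analysis plan that is not shown may set one. Nor is there a replacement rule: the total is fixed at 160, and section 7.10 ends the study with patient 160.

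A second tempting reading is that Appendix 1 gives infinity to every failure over the allocated bougie. It gives it only to impossible intubation. The scale adds points for extra attempts, extra operators, alternative techniques and other manoeuvres. A patient in whom the allocated bougie failed but who was intubated another way may therefore have a finite score.

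Third, the large differences rest on an assumed 8% against 1% imbalance. With rare and equal failures the handling hardly matters, and with equally common failures ranking them worst costs power.

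All three objections stand and limit the point. They do not remove the conflict: sections 7.3 and 8.1 still budget failures as losses, section 2.3 still ends data collection when a poor score is most likely, and Appendix 1 still supplies a score. A separate analysis plan could define the analysis set, but it could not recover scores that were never recorded.

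**Conclusion.** The point holds as a conflict between passages that puts the primary comparison at risk. It does not show that outcomes will certainly be dropped. Followed as written, sections 2.3, 7.3 and 8.1 would lose results that depend on the allocated bougie and that Appendix 1 and the rank test could use.

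On the assumed failure rates, the effect runs from about 2 percentage points of power (2% in both arms) to between 20 and 30 points (8% against 1%), in either direction according to which arm fails more. These figures also rest on the rounded-normal score model and on treating every failure as worst-ranked. Patients given a finite score after another technique would have less influence. The change is worth making before any outcome data are seen.

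**What to change.** - In sections 7.3 and 8.1, remove failures from the reasons for the reserve. Keep the 14 places for cancelled surgery, withdrawal and truly missing data, in line with section 8.8.
- Reconcile the end of data collection in section 2.3 with Appendix 1, so that the mIDS is still recorded for these patients. This concerns recording only, not clinical management.
- State that every randomised patient in whom laryngoscopy is started is analysed in the allocated arm, with impossible intubation given the highest rank.
- Prespecify one scoring rule for patients intubated by another technique after the allocated bougie failed: either the finite Appendix 1 score or the highest rank. The second choice extends what Appendix 1 now says, so it must be written down as such.

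The cost is a few sentences, and the recruitment target of 160 need not change. There are two downsides. Means cannot be reported with infinite scores, so medians and counts by difficulty category would be shown instead. If failures are equally common in both arms, power is lower than with failures dropped: about 0.79 against 0.90 at 8.75% in each arm.

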8.2 Planned recruitment rate

[figure not shown]
We are planning to recruit 160 participants over 18 months. The planned recruitment rate is 4 to 5 participants per week.

Statistical analysis plan

[figure not shown]
8.3.1 Summary of baseline data and flow of patients

The normally distributed base line data such as age, gender, weight and airway assessment parameters between two groups will be compared using students t test. Statical significance is taken as p value <0.05.

CONSORT Flow Diagram

Flow of participants through the study

8.3.2 Primary outcome analysis

Primary outcome is modified intubation difficulty scale score (mIDS). Non parametric test either Mann-Whitney U test or Kruskal- Wallis test would be used, as appropriate.

8.3.3. Secondary outcome analysis

The sample size is based on primary outcome.

8.4 Subgroup analyses

Not applicable

8.5 Adjusted analysis

Not applicable

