| Chief Investigator | [name] Department of Anaesthesia University Hospital, Coventry, [name] Contact no: [name] [name] |
| Principle Investigator | [name] Department of Anaesthesia University Hospital, Coventry, [name] Email: [contact] |
| Co-investigators | [name], [name] Department of Anaesthesia University Hospital, Coventry, [name] Contact number [name] Email [contact] |
| Sponsor | University Hospitals Coventry & Warwickshire NHS Trust |

[figure not shown]
TRIAL SUMMARY

| | | |
|-----------------------------|---|--|
| Full study title | A randomised comparison between standard and flexible tip bougie (tracheal tube introducers) for tracheal intubation using non channelled videolaryngoscope | |
| Short study title | Standard vs flexible tip bougie for videolaryngoscopy | |
| Trial Design | Randomised control Trial | |
| Trial Participants | Patients aged 18 and above, presenting for elective surgical procedures where tracheal intubation is indicated | |
| Planned Sample Size | 160 | |
| Follow up duration | 3 to 24 hours | |
| Planned Trial Period | 18 months | |
| | Objectives | Outcome Measures |
| Primary | Ease of tracheal intubation | Modified Intubation Difficulty Scale Score |
| Secondary | Success rate at first attempt | Laryngoscopy time Intubation time Additional manoeuvres required Bougie impingement Bougie rotation Post op sore throat between 3 -24 hours post op Success of tracheal intubation |

Key Words: Intubation; tracheal, airway device; video laryngoscope

STUDY FLOW CHART

Figure 1: Flow of participants through the study

SCHEDULE OF OBSERVATIONS

Table 1: Schedule of Events

| Procedure | Screening | Baseline | Pre-Op | Intra-Op | Post-Op |
|--|-----------|----------|--------|----------|---------|
| Eligibility assessment | X | X | | | |
| Informed consent | | X | | | |
| Demographic data (DOB, sex, height and weight) | | X | | | |
| Details regarding operative procedure, Anaesthesia and method of airway management | | | X | | |
| Airway Assessment | | | X | | |
| Randomistaion | | | | X | |
| Laryngoscopy, Tracheal Intubation Laryngoscopy time, intubation time and modified intubation difficulty score | | | | X | |
| Post op visit- sore throat | | | | | X |

Contents

| | |
|---|----|
| SIGNATURE PAGE..... | 2 |
| Key Words: Intubation; tracheal, airway device; video laryngoscope..... | 4 |
| LIST OF ABBREVIATIONS | 9 |
| 1. INTRODUCTION | 10 |
| 2. RATIONALE | 12 |

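### Section 8.5 plans no adjusted analysis, although airway measures recorded before randomisation could add modest power to the mIDS comparison at no cost in patients

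*Protocol*

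**What the plan says.** The entry under "8.5 Adjusted analysis" in the protocol is "Not applicable". For the primary outcome, section 8.3.2 states: "Non parametric test either Mann-Whitney U test or Kruskal- Wallis test would be used, as appropriate". Neither test takes covariates. Section 8.9 adds: "There is no plan to deviate from original statistics". The protocol has therefore made this choice itself and has not left it to a later analysis plan.

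Section 7.6 lists the baseline data, which include BMI, and continues: "Airway assessment includes Mallampati score, thyromental distance, mouth opening, jaw protrusion and neck movement". It describes their origin as follows: "This is the routine assessment undertaken by the anaesthetists as a part of standard preoperative airway assessment". In Table 1 the airway row ("Airway Assessment | | | X") is marked in the Pre-Op column and the randomisation row ("Randomistaion | | | | X") in the Intra-Op column. Height and weight are marked at Baseline. Section 7.3 describes sealed envelopes and mentions no stratification.

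**The concern.** Anatomy varies between patients and may move mIDS whichever bougie is used. Appendix 1 scores glottic view, lifting force and external laryngeal pressure. All three belong to laryngoscopy, and section 7.3 has the bougie passed only after laryngoscopy. Eligibility in section 6 is broad and the randomisation is not described as stratified, so anatomy is left to vary within and between arms.

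If the recorded measures predict mIDS, an unadjusted test leaves that variation in the error term and gives up some power. Section 8.3.1 compares airway parameters between arms at p<0.05 but attaches no consequence to the result. An adjustment brought in after seeing such a p value would be post hoc. If adjustment is to be used, it has to be fixed beforehand.

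**Working it through.** **Inputs.** From section 8.1: control mean 1.75, SD 0.95, a 30% reduction, standardised difference 0.53, power 0.9, significance level 0.05, 73 per group (146 in all), 160 recruited. Two-sided testing is assumed, as the protocol does not say. R² is not in the protocol; the range 0 to 0.3 is an assumption.

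**The plan's own figure.** n per arm = 2(1.960 + 1.282)²/d².
- With d = 0.53: 74.8, so 75, against 73 stated. This is close enough to count as reproduced.
- With the raw inputs: 0.30 × 1.75 = 0.525 and 0.525/0.95 = 0.553, giving 69. Dividing 69 by 0.955, the efficiency of the Mann-Whitney test under normality, gives 72.3, so 73.
- The power of a t-test at 73 per arm is 88.9% for d = 0.53 and 91.3% for d = 0.553. At 80 per arm it is 91.5% and 93.5%.

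The trial thus reaches about 90% power without adjustment.

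**Effect of adjustment on power.** In a linear model the residual SD becomes 0.95 × √(1 − R²), so d becomes d/√(1 − R²). The first power column starts from exactly 90% at 73 per arm (d = 0.540, t-test). The second uses the raw inputs (0.525 and 0.95, normal approximation).

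| Assumed R² | Power from 90% | Power from raw inputs | √(1 − R²) | 146/(1 − R²) |
|---|---|---|---|---|
| 0 | 90.0% | 91.6% | 1 | 146 |
| 0.1 | 92.7% | 94.1% | 0.949 | 162 |
| 0.2 | 95.2% | 96.2% | 0.894 | 183 |
| 0.3 | 97.2% | 97.9% | 0.837 | 209 |

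At R² = 0.3 the gain is 97.2 − 90.0 = 7.2 points, or 97.9 − 91.6 = 6.3 points. At R² = 0.05 the raw inputs give 92.9%, a gain of 1.3 points.

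**Check with rank methods.** The table is a linear approximation, so the planned type of test was simulated on discrete scores with control mean 1.75 and SD 0.95, four covariates and 73 per arm. Under one assumed score distribution Mann-Whitney power was about 87%, and rank ANCOVA gave 89%, 91% and 94% at R² = 0.1, 0.2 and 0.3. Under another, Mann-Whitney gave 91% to 92% and rank ANCOVA 93%, 95% and 96.5%. Type I error was about 5% in both. With R² = 0, adjustment lowered power from 91.6% to 91.1%. Absolute power depends on the assumed distribution; the direction and rough size of the gain do not.

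**Chance imbalance.** The part of the arm difference due to covariate imbalance has SD √R² × 0.95 × √(2/73). That is 0.035 points at R² = 0.05 and 0.086 at R² = 0.3, against a target difference of 0.525.

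**The case against.** The strongest reply is that nothing here is wrong. An unadjusted comparison of randomised arms is valid, sections 8.3.2 and 8.5 agree with each other, and the sample size was set without adjustment and meets its target. All of that stands.

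The second reply is that R² may be close to zero. Appendix 1 also scores bougie impingement, bougie rotation, subglottic tube impingement and tube rotation. These are largely bougie and tube events, and section 2.2 attributes impingement to the rigid, fixed tip. Every patient has a videolaryngoscope, and those needing awake intubation are excluded. This also stands, and it is why the range must start at zero.

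Three stronger readings are tempting, and the documents do not support them:
- A reader might infer that the airway measures were chosen as predictors of difficulty. Section 7.6 presents them as routine care, and no correlation with mIDS is given.
- A reader might infer that chance imbalance biases the result. It does not; the type I error already allows for it.
- A reader might take √(1 − R²) to mean intervals 5% to 16% narrower under any adjusted model. That holds for a mean difference in a linear model. In a proportional-odds model the standard error of the log odds ratio rises: in a small check (80 fits per setting) its median went from 0.314 to 0.327 at R² = 0.1 and from 0.313 to 0.335 at R² = 0.3. Power rises there because the estimate moves away from the null.

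None of this removes the point that data already collected could be used at almost no risk.

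**Conclusion.** The point holds as missed efficiency. Adjustment is applicable, because suitable covariates are recorded before randomisation and some mIDS components plausibly depend on anatomy. At 73 per arm it would change power by between about half a point lost (R² = 0) and 6 to 7 points gained (R² = 0.3). The gain rests wholly on an R² that the protocol does not supply, and on an approximation that the simulations support in direction and rough size. The planned analysis is neither invalid nor underpowered for want of adjustment, and it should not be described so.

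**What to change.** Replace the entry in section 8.5 with one pre-specified method and align section 8.3.2 with it. For example:

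> *The primary comparison of mIDS uses rank ANCOVA, with impossible intubation given the highest rank, adjusted for Mallampati score, mouth opening, thyromental distance, neck movement and BMI as recorded before randomisation. The adjustment is made regardless of any observed imbalance. The unadjusted Mann-Whitney U test is reported as a sensitivity analysis.*

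The covariate list is an example; what matters is that it is short, fixed in advance and has its coding stated. One model should be named, not a choice between models. Strata for the operator should not be added, as their number is unknown. If the sponsor prefers to keep Mann-Whitney as primary, the same rank ANCOVA should be pre-specified as supportive.

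The cost is wording in two sections, with no extra patients or assessments. The downsides are a modest model assumption, which the sensitivity analysis covers, and about half a point of power if the covariates turn out not to be prognostic.
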